7.4 Research Question

DORA was developed to provide an alternative for conducting post-cataract surgery follow up assessments to save nurses' and other clinicians' time. The key outcome of this study is evaluating **DORA's** ability to accurately identify which patients have postoperative complications which would justify specialist care, and assessing **DORA's** accuracy compared to an expert clinician. To assess this critical capability, the research question that this study will investigate is: Can **DORA** identify which patients need clinical follow up after a cataract operation?

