8.2.5.2 Secondary Outcomes

There will be several secondary outcome measures to assess the clinical safety, feasibility, usability, and acceptability of the system (see Table 6).

Clinical safety

To examine safety, two outcomes will be captured. Firstly, patients at both sites will have a retrospective case review of both general and ophthalmic electronic health records at 90 days after their initial operation. Complications will be identified from patient's medical records related to any unplanned eye-related clinical episode.

Secondly, all cataract surgery patients at Imperial were historically followed up face-to-face between 3-4 weeks post-surgery in a dedicated post-op clinic. Any complications requiring a change in patient management at slit lamp review or from attending eye casualty services (as the Oxford site does not normally perform face-to-face follow-ups) will be compared with the decisions made by **DORA** and the clinician. If Imperial changes their method of follow-up due to the COVID-19, assessment for complications will be done by checking hospital medical records as is done at the Oxford site.

Feasibility

Feasibility will be assessed by examining the proportion of autonomous calls that were completed without needing any intervention from the supervising clinician. All interruptions or clarifying questions of the supervised call will be logged; the supervising clinician will be asked to log the reason for asking clarifying questions. If clarifying questions were asked because the clinician felt that there was insufficient information for either individual symptoms or to make a management plan, the clinician's management plan before and after clarifying questions will be captured to see if clarifying questions changed the management plan.

Usability

Usability will be assessed using questions presented to patients following calls delivered by online and paper surveys distributed to participants. These questions will be drawn from the System

Usability Scale (SUS) and Telehealth Usability Questionnaire (TUQ; see 13.4 Appendix 4 for a sample survey) [14,15].

Acceptability, satisfaction, and appropriateness

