13.6 Appendix 6. Imperial Historical Recruitment Audit Data

Purpose

To provide real world evidence for assumptions made in modelling of recruitment numbers and study planning.

Audit

We audited all bookings in the cataract one-stop-clinic for the month of October 2020. After discussion with the head of the cataract pathway, it was felt this was the most representative of what the cataract pathway will likely look like in May-July 2021 assuming there is COVID recovery of a similar trajectory to the first wave. It is anticipated there will be 3 consultant-led one-stop clinics running in July to address the backlog. Of note, the general pre-assessment pathways have not been audited.

Key findings

Clinic capacity and utilisation - All October one-stop data

- 33 patients were booked across 4 clinics
- 8.25 patients on average per clinic
- 88% (29/33) attended their one-stop appointments

Conversion rate

- Of all patients booked, 76% proceeded for surgery (25/33)
- Or, of those attending, 86% proceeded to surgery (25/29)

Demographics

- Mean age was 71.5
- This was the first eye for 52% of patients

Inclusion/Exclusion

- 100% (29/29) of those attending were listed for routine cataract surgery
- 10% (3/29) required a translator (Tamil, Punjabi, Arabic)
- 1 patient (3%) had dementia and would not have been able to consent
- Overall, of all attending patients, 76% (29/33) would have been eligible for trial inclusion.

Withdrawal

- No patients in this cohort had unexpected surgical complications
- 1 patient (4%) attended AnE before follow up with a corneal abrasion and would have been withdrawn from **DORA** per our current protocol.

Follow up

- 95% (24/25) of patients attended post-op follow up
- **21%** (7/25) of patients had a documented complication requiring management change at their post-op followup.
 - \circ 6 of these patients were uveitis
 - 4 of which were given maxidex and discharged
 - 1 was given maxidex with phone follow up

- 1 was given maxidex and listed for 2nd eye.
- 1 patient has post-op cystoid macular oedema and maxidex requiring medical retina review.

Pathway

- The mean time between one-stop appointment and surgery was **9.88 days.**
 - The range was from 2 days to 62 days
 - **16 patients** had their operations in under 1 week
- Mean time between surgery and first follow up was 24.33 days.
- A number of patients were followed up under the 21 day point

Comparison with initial estimates

| | Imperial | Imperial |

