A Clinical Investigation of an Autonomous Phone Conversational Agent for Cataract Surgery Follow-up

NCT05213390

30 August 2022

Statistical analysis plan

Using the variables:

- doraoutcomeupdate (0 = pass, no review, 1 = fail, needs review)
- supervisoroutcomeupdate (0 = pass, no review, 1 = fail, needs review)

Primary outcome: Agreement between Dora and clinician for overall outcome decision and each symptom (x5)

- Inter-rater reliability (kappa)
- Accuracy (%)
- Data regarding true/false negatives/positives

	Clinician: follow-up (1)	Clinician: no follow-up (0)
Dora: follow-up (1)	ТР	FP
Dora: no follow-up (0)	FN	TN

• Sensitivity, specificity, AUC

Secondary outcomes

Clinical safety: Comparison with real complication rate

*Note: please do this analysis three times, once for each of the three complication measures
Data regarding true/false negatives/positives (Tables 2-3)

	Complications: 3 month audit	No complications: 3 month audit
Dora: follow-up	ТР	FP
Dora: no follow-up	FN	TN

- Sensitivity, specificity, AUC
- Variables
 - Dora follow up: "doraoutcomeupdate"
 - Complications:
 - "hospital-review-within-3-months"
 - 0 = no hospital review, 1 = hospital review
 - "unexpected-change-management"
 - 0 = no unexpected change management, 1 = unexpected change management

EUR ING [name] MA MSc MBA MPA PhD CEng FBCS Associate Professor of eHealth

"unplanned-hospital-rev"

• 0 = no hospital review, 1 = hospital review

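### Two of the SAP's three complication variables record attendance without a finding, so their safety tables do not give sensitivity and specificity for postoperative complications

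*SAP*

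**What the plan says.** The SAP, under Secondary outcomes (Clinical safety), compares DORA with the real complication rate. DORA's decision forms the rows of a 2x2 table. The columns are headed as complications and no complications at the three-month audit. Sensitivity, specificity and AUC follow. The analysis is run once for each of three variables:

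- `hospital-review-within-3-months`, coded "0 = no hospital review, 1 = hospital review";
- `unexpected-change-management`, coded "0 = no unexpected change management, 1 = unexpected change management";
- "unplanned-hospital-rev", with the same coding as the first.

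The SAP defines none of the three further. No coding mentions a finding, a cause or a link to the operation.

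Protocol 7.4 is concerned with whether DORA can "accurately identify which patients have postoperative complications which would justify specialist care", and its research question is whether DORA can "identify which patients need clinical follow up after a cataract operation". Objective 2 in 7.5 is baseline sensitivity and specificity for detecting patients with postoperative complications.

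Protocol 8.2.5.2 describes the safety events. For the record review: "Complications will be identified from patient's medical records related to any unplanned eye-related clinical episode". For the face-to-face visit or eye casualty, the event is a complication for which management had to be changed. Section 8.5.1 adds that patients presenting to the eye service are looked at one by one, to separate what DORA missed from what developed later. It says the resulting sensitivity and specificity will serve later evaluations.

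**The concern.** In 8.2.5.2 the unplanned episode is the place to look and the complication is the event. In two of the SAP's three tables the episode itself has become the event. A patient who comes in worried and is found normal enters the complications column. If DORA passed that patient, a correct decision is scored as a miss.

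This matters because, in the SAP, these tables are the only comparison of DORA with what happened after the call. The primary analysis uses the supervising clinician, who under 8.2.5.1 decides from the same call. A complication that the call did not bring out can be missed by both. The safety sensitivity is also the figure that 8.5.1 hands on to later studies.

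**Working it through.** The plan has no figure of its own to reproduce here. The documents state no expected sensitivity, no flag rate, and no share of unplanned reviews that find nothing.

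**Step 1: where each patient falls.** The table follows the SAP coding as written and compares it with a column defined by a surgery-related complication.

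| DORA | Review took place | Finding | Attendance table | Complication table |
|---|---|---|---|---|
| pass | yes | complication | FN | FN |
| pass | yes | none | **FN** | **TN** |
| flag | yes | complication | TP | TP |
| flag | yes | none | **TP** | **FP** |
| pass | no | none recorded | TN | TN |
| flag | no | none recorded | FP | FP |

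The second and fourth rows differ. Both arise only because attendance is read as a complication.

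**Step 2: size of the effect on sensitivity.** Let S be the chance that DORA flags a patient with a complication, f the chance that it flags one without, and c the share of reviews that find a complication. Then

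reported sensitivity = c × S + (1 − c) × f.

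Assumed, not taken from the documents: S = 0.80, f = 0.10, and c from 0.25 to 0.75.

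- c = 0.75 (25% of reviews find nothing): 0.75 × 0.80 + 0.25 × 0.10 = 0.625
- c = 0.50: 0.50 × 0.80 + 0.50 × 0.10 = 0.450
- c = 0.25 (75% find nothing): 0.25 × 0.80 + 0.75 × 0.10 = 0.275

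The true value is 0.80 throughout. It is recovered only at c = 1, when every review finds a complication.

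**Step 3: specificity.** Suppose every complication leads to a recorded review and f is the same in attenders and non-attenders. Reported specificity is then 1 − 0.10 = 0.90, which is correct, and the error falls on sensitivity. If patients flagged without a complication attend more often than those passed, the fourth row grows and the sixth shrinks, so reported sensitivity and specificity are both higher than under equal attendance. The direction of the error is therefore not fixed.

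**Step 4: the third variable.** The second safety event in 8.2.5.2 has two parts: a complication, and a change of management because of it. The SAP variable has the change, qualified as unexpected, but does not mention a complication. The Imperial audit in Appendix 6 uses the two-part event. It describes seven patients: "4 of which were given maxidex and discharged", one had phone follow-up, one was listed for the second eye and one needed medical retina review (4 + 1 + 1 + 1 = 7). On a plain reading all seven fit both definitions. What cannot be told is whether a change unrelated to the operation would also be coded 1.

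**The case against.** **The three tables check each other.** A patient found normal, with no change of management, is a false negative in the attendance tables only, so a careful reader could see the discrepancy. That is true, but two of the three tables would still report attendance under a complication heading, with a sensitivity attached.

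**The case review in 8.5.1 still applies.** A short SAP does not withdraw it, and it may have informed how the fields were filled. The documents cannot exclude this. The stated coding is nevertheless review or no review, and an analyst following it would use that.

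**The two attendance variables are not alike.** This stands. "unplanned-hospital-rev" follows the unplanned episode of 8.2.5.2 and is the better proxy. The broader variable might also count Imperial's routine visit (8.2.4), and the SAP does not say. Neither carries a finding.

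**Stronger readings that the documents do not support.**

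- A reader might infer that none of the three variables measures a complication. The management-change variable tracks the protocol's own safety event closely, so its fault is a missing definition.
- A reader might infer from "postoperative complications which would justify specialist care" in 7.4 that only the one audit patient in seven sent for medical retina review should count, and that pooling all seven distorts sensitivity. The documents set no such threshold. The research question is about need for follow-up, 8.2.3 about whether specialist review is required, and 8.2.5.1 about need for clinical assessment. A complication found and treated at a visit can meet all of these. Between one and seven of the seven could qualify, depending on a definition that is not given, and a single patient cannot support a rate.
- A reader might infer that 7.4 goes unanswered. Section 7.4 also asks for accuracy against an expert clinician, and the SAP's primary analysis gives sensitivity and specificity against the supervising clinician.

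**Conclusion.** The point holds for the two attendance variables. Followed as written, their tables measure how DORA's decision relates to attending hospital, not its sensitivity and specificity for postoperative complications under objective 2. Running the analysis three times does not repair them. The management-change variable has a smaller fault: it needs to be tied to a complication of surgery.

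The misclassification follows from the coding alone. Its size does not. The range of about 63% down to 28%, against a true 80%, rests on an assumed sensitivity, an assumed 10% flag rate and an assumed 25% to 75% of reviews finding nothing. It also assumes that, given complication status, DORA's flag is unrelated to attending. It shows that the effect can be large and is not a forecast. The change should be made, although these are secondary tables and the primary agreement analysis is unaffected.

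**What to change.** 1. From the record review in 8.5.1, code one variable per patient: 0 = no surgery-related complication found, 1 = surgery-related complication found. Use it as the complication column of the safety 2x2 table.
2. Define `unexpected-change-management` by the second safety event in 8.2.5.2, so that it is 1 only when the change was made for a complication of the surgery. Keep it as the second reference.
3. Report `hospital-review-within-3-months` and "unplanned-hospital-rev" as utilisation counts, without sensitivity, specificity or AUC. State whether Imperial's routine visit is included in the first.
4. If wanted, add a descriptive breakdown of complications by what followed. Do not make a reference standard that counts only those sent on for further specialist care.

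The cost is a change to the SAP wording and one field in a review that is already planned. The downside is fewer events than in the attendance tables, and so wider intervals.
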